### **9.4.3. Safety Analyses**

The principal analysis will be based on the safety evaluable population, according to treatment assignment.

Adverse events will be coded by the MedDRA, and incidences will be tabulated by preferred term and system organ class for all events, related events, events ≥ Grade 3 and adverse events of special interest. Severity of AEs will be based on the CTCAE scale as indicated in Section 8.1.1. Quantitative safety variables and their changes from baseline (laboratory, vital signs) will be summarized with descriptive statistics. Clinically significant abnormal values will be flagged and tabulated based on predefined criteria.

Exposure will be analyzed by describing dose intensity, which is defined as the dose-received divided by the dose planned over a given time interval. This will be done by cycle as well as overall cycles received for MK-3475 + INCB024360. The percentage of subjects with any delay and/or reduction will also be calculated.

The clinical laboratory data will be analyzed using summary statistics (eg, means and frequencies), and no formal statistical comparisons among the treatments are planned. In addition, these values will also be classified into CTCAE toxicity grades and tabulated. Descriptive statistics and mean change from baseline will be determined for vital signs at each assessment time. Vital sign results will be reviewed for clinically notable abnormalities.

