8.3.2. Laboratory Value Summaries

Clinical laboratory tests, including hematology and serum chemistry (see Appendix A), will be performed for each subject during the study in accordance with Table 13 in Protocol Amendment 10.

If specific safety issues arise, additional unscheduled laboratory tests/analyses may be performed at the discretion of the investigator.

All test results and associated normal ranges from central laboratories will be reported in SI units. All tests with numeric values will have a unique unit per test. Any laboratory test results and associated normal ranges from local laboratories will be converted to SI units. For the limited number of cases where the associated normal ranges from a local laboratory cannot be obtained despite due diligence, a set of standard normal ranges based on documented reference ranges will be applied to facilitate reporting the test results.

Laboratory parameters identified in Table 10 will be summarized. Shift tables based on worst postbaseline value recorded will use all postbaseline values. Other laboratory parameters collected will only be listed in an appendix to the Clinical Study Report in their original units without SI conversions. A detailed listing of the serum chemistry, hematology, and urinalysis tests is provided in Appendix A.

Panel	Parameter
Serum chemistry	Albumin, alkaline phosphatase ^{a,b} , ALT ^{a,b} , AST ^{a,b} , amylase, bicarbonate, BUN, calcium, chloride, creatinine, glucose, iron, lactate dehydrogenase, phosphorus, potassium, serum or plasma lipase, sodium, total bilirubin ^{a,b} , direct bilirubin, total protein, uric acid
Lipid	Total cholesterol, triglycerides, LDL, HDL, CRP ^b
Hematology	Hemoglobin, hematocrit, platelet count, red blood cell count, reticulocyte count, WBC ^b , basophils, eosinophils, lymphocytes ^b , monocytes, neutrophils ^b
Endocrine monitoring	ACTH ^c , serum cortisol ^c , LH, prolactin ^c , TSH ^c , free T4 ^c , T3 ^c , serum testosterone ^c
Urinalysis	Color and appearance, pH and specific gravity, bilirubin, glucose, ketones, leukocytes, nitrite, occult blood, protein, urobilinogen
Pregnancy test	Female subjects of childbearing potential only require a serum test at screening; pregnancy tests (serum or urine) should be repeated if required by local regulations
Coagulation	PT, aPTT, INR

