Serology	HBsAG, HBsAG antibody, HBc, HCV antibody, HCV-RNA, HBV-DNA, HCV genotype, HCV viral load (for subjects with HCC only), anti-HDV, anti-HBe, HBV viral load, anti-HBc (total), HBeAg (for subjects with HCC who are HBsAg+ or anti-HBc+, anti-HBs-, HBsAg- viral load < 100 IU/mL only)
Other	CA 125 (ovarian cancer only), CEA (gastric cancer only), AFP (HCC only)

Table 10:Laboratory Parameters To Be Summarized

^a Summaries of LFTs will be performed on a weekly basis instead of by cycle.

^b Line graph and box-and-whisker plots will be provided.

^c Only normal-high-low shift tables will be provided.

Numeric laboratory values will be summarized descriptively, and non-numeric test values will be tabulated.

For test results that will be summarized with available normal ranges, the number and percentage of subjects with the laboratory values being low (but never high), normal, high (but never low), and both low and high will be calculated for each test. Laboratory values with greater than or less than signs will require medical monitor review. Laboratory ranges with greater than or less than signs will be handled as follows: if only an upper limit exists, for example, < 200, then the range will be (0,199.99); similarly, if only the lower limit exists, for example, > 0, then the range will be (0.001, 9999).

This shift summary will be produced for each test for the safety population. The denominator for the percentage calculation will use the number of subjects in the baseline category (ie, low, high, normal, missing) as the denominator for the percentage in each of the categories during the treatment period.

For all gradable laboratory parameters identified in Table 10, the values will be classified into grade levels corresponding to CTCAE v4.03 criteria. For specific laboratory values requiring clinical intervention to grade, the classification according to the quantitative component will be provided. See Appendix B for laboratory grading criteria.

The number and percentage of subjects with the laboratory values of Grade 1, 2, 3, or 4 will be calculated for each treatment according to the largest treatment-emergent worsening of

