10.1. Changes to Protocol-Defined Analyses

Study enrollment was permanently discontinued on 17 MAY 2018 as a strategic decision. This decision was made following the recommendation of the external Data Monitoring Committee of the INCB 24360-301 blinded melanoma clinical study, which determined that the study did not meet the prespecified endpoint of progression-free survival improvement for the combination of pembrolizumab + epacadostat compared with pembrolizumab + placebo; in addition, the overall survival (OS) endpoint was not expected to reach statistical significance. Of note, there were no new safety concerns identified in either arm of the melanoma study.

Due to this strategic decision, Protocol-defined analyses were reduced. Efficacy analyses will only be performed for primary and secondary endpoints

See Appendix E for a detailed list of outputs that will be included in the abbreviated CSR for both safety and efficacy.

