3.2.19	Summary of Treatment-Emergent Adverse Events Leading to Any Dose Interruption by MedDRA System Organ Class and Preferred Term	Safety Evaluable	X
3.2.20	Summary of Treatment-Emergent Adverse Events Leading to Discontinuation of Any Study Drug by MedDRA System Organ Class and Preferred Term	Safety Evaluable	X
3.2.27	Summary of Treatment-Emergent Adverse Events of Special Interest by Category and MedDRA Preferred Term	Safety Evaluable	X
3.3 Labora	atory		
3.3.1.1	Summary of Laboratory Values - Hematology	Safety Evaluable	Х
3.3.1.2	Summary of Laboratory Values - Chemistry	Safety Evaluable	Х
3.3.1.3	Summary of Laboratory Values – Endocrine Monitoring	Safety Evaluable	Х
3.3.2.1	Shift Summary of Hematology Values - to the Worst Abnormal Value	Safety Evaluable	X
3.3.2.2	Shift Summary of Chemistry Values - to the Worst Abnormal Value	Safety Evaluable	Х
3.4 Vital S	igns		
3.4.1	Summary of Systolic Blood Pressure	Safety Evaluable	Х
3.4.2	Summary of Diastolic Blood Pressure	Safety Evaluable	Х
3.4.3	Summary of Pulse	Safety Evaluable	Х
3.4.4	Summary of Body Temperature	Safety Evaluable	Х
3.4.5	Summary of Respiration Rate	Safety Evaluable	Х

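### SAP Appendix E lists no laboratory table by CTCAE grade, although SAP 8.3.2 and Protocol 9.4.3 require one and SAP 10.1 does not record it as dropped

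*SAP*

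**What the plan says.** **The requirement.** After the descriptive laboratory summaries, Protocol 9.4.3 states: "In addition, these values will also be classified into CTCAE toxicity grades and tabulated". SAP 8.3.2 turns this into a procedure: "For all gradable laboratory parameters identified in Table 10, the values will be classified into grade levels corresponding to CTCAE v4.03 criteria". It continues: "The number and percentage of subjects with the laboratory values of Grade 1, 2, 3, or 4 will be calculated for each treatment". Subjects are counted by their largest treatment-emergent worsening. High and low abnormalities are kept apart where both are graded, and a glucose example shows the rule at work. SAP Appendix B holds the cut-points.

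**The shift summary.** SAP 8.3.2 also describes a different display, classified against the normal range. "Shift tables based on worst postbaseline value recorded will use all postbaseline values". Postbaseline results are classed as low, normal, high, or both low and high, and percentages use the "number of subjects in the baseline category (ie, low, high, normal, missing) as the denominator".

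**The output list.** SAP 10.1 says that Protocol-defined analyses were reduced and then: "See Appendix E for a detailed list of outputs that will be included in the abbreviated CSR for both safety and efficacy". The laboratory block of Appendix E contains:

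- Tables 3.3.1.1 to 3.3.1.3: descriptive summaries for hematology, chemistry and endocrine tests.
- Table 3.3.2.1: "Shift Summary of Hematology Values - to the Worst Abnormal Value".
- Table 3.3.2.2: "Shift Summary of Chemistry Values - to the Worst Abnormal Value".

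The relevant subject-level listings are 2.7.3 (the Hy's Law pattern), 2.8.1.1 and 2.8.1.2 (hematology and chemistry values) and 2.8.2 (abnormal values).

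**The concern.** The body of the SAP promises an analysis that its own output list does not show. Programming normally follows the list, so the graded tables may simply not be produced.

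This matters because clinical laboratory evaluation is part of the Phase 1 primary endpoint (Protocol 4.2.1, SAP 2.3.1). The DLT criteria (Protocol Table 5), the dose-modification rules (Table 6) and the hepatic rules (Table 8) are also written by grade.

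AE tables cannot fully stand in. Under Protocol 8.1.1 a laboratory abnormality is an AE only if it causes signs or symptoms, is judged clinically meaningful, needs therapy or changes study drug. A high value that meets none of these conditions never reaches an AE table. The AE tables that select on severity (3.2.6 and 3.2.7) also pool Grade 3 with anything higher, whereas Protocol Table 8 treats asymptomatic Grade 3 and Grade 4 lipase or amylase differently. Lipase is a live example: Protocol 1.3.3 reports treatment-related Grade 3/4 lipase increase in 12 subjects (4%), the most frequent such event listed there for Phase 2 subjects at 100 mg BID.

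**Working it through.** The plan states no figure to reproduce. The check compares the requirement with the output list and then asks what the listed tables can show.

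**Step 1. Match each requirement to an output.**

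| Required by | Content | Matching title in Appendix E |
|---|---|---|
| SAP 8.3.1, 8.3.2 | Values and change from baseline, descriptive | 3.3.1.1, 3.3.1.2, 3.3.1.3 |
| SAP 8.3.2 | Shift to worst postbaseline value | 3.3.2.1, 3.3.2.2 |
| SAP 8.3.2, Protocol 9.4.3 | Subjects by CTCAE laboratory grade | none |

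Laboratory tables titled by grade: 0 of 5.

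**Step 2. Count the parameters affected.** These appear in SAP Table 10 and also have a row in Appendix B.

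- Chemistry, 14: albumin, alkaline phosphatase, ALT, AST, amylase, calcium, creatinine, glucose, phosphorus, potassium, lipase, sodium, total bilirubin, uric acid.
- Hematology, 5: hemoglobin, platelets, white cells, lymphocytes, neutrophils.
- Lipid, 2: total cholesterol, triglycerides.
- Coagulation, 2: aPTT, INR.

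14 + 5 = 19 in the two panels that have shift tables, and 19 + 2 + 2 = 23 in all.

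**Step 3. See what a normal-range shift table merges.** Appendix B cut-points, in multiples of ULN:

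| | Grade 1 | Grade 2 | Grade 3 | Grade 4 |
|---|---|---|---|---|
| ALT, AST | > 1 to 3 | > 3 to 5 | > 5 to 20 | > 20 |
| Lipase | > 1 to 1.5 | > 1.5 to 2 | > 2 to 5 | > 5 |

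If the shift tables use the layout in 8.3.2, all four grades fall in the single category high. ALT of 1.1 × ULN (Grade 1) and 25 × ULN (Grade 4) would share a cell.

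**Step 4. Ask where severity would still show.**

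- Listings 2.7.3, 2.8.1.1, 2.8.1.2 and 2.8.2 give subject-level data.
- The descriptive tables include the maximum and minimum (SAP 5.1).
- AE tables, and DLT Listing 2.7.4, cover abnormalities reported as AEs.

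None of these is a count of subjects by laboratory grade. To obtain one, a reader would have to tally listings for several hundred subjects: 356 were enrolled by 27 FEB 2017 (Protocol 1.1.4), against about 508 planned (Protocol 4.4).

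**Step 5. Ask whether the omission is recorded.** The visible text of SAP 10.1 specifies only the efficacy reduction and refers to Appendix E for the rest. SAP 8.5 says outright which ECG outputs go into the abbreviated CSR. SAP 8.3.2 has no such statement and still says that grading will be done.

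**The case against.** **The shift tables may already be graded.** Their titles give no categories. Appendix E marks them as standard tables, laid out according to a separate set of standard safety tables that is not supplied. SAP 8.3.1 mentions CTCAE severity shortly before it mentions shift tables. A footnote to Table 10 restricts most endocrine tests to normal-high-low shifts, which suggests that other panels get something more. This stands as a real uncertainty: the low/normal/high layout is inferred from 8.3.2, not read from the titles. The footnote does not settle it, because it does not say which output holds the grades. It also already disagrees with Appendix E, which lists an endocrine value summary and no endocrine shift table.

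**The omission may be deliberate.** SAP 10.1 declares a general reduction and refers to Appendix E for safety as well as efficacy. Documenting reductions is Amendment 4's stated primary purpose, and gaps in the AE table numbering look like pruning. The efficacy sentence in 10.1 also ends abruptly, so text may have been removed. All of this is fair. Even so, 8.3.2 would then be out of step with the output list.

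**A reader might infer that the report could not tell a trivial liver or lipase rise from a Grade 4 one.** The documents do not support that. The listings and descriptive extremes show magnitude.

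**A reader might also infer that nothing would show how often the DLT or discontinuation thresholds were reached.** That is too strong as well. A DLT is by definition a treatment-emergent AE (Protocol 5.5.1) and has its own listing. Protocol Table 8 makes Grade 3-4 AST, ALT or bilirubin a discontinuation event, and a value that changes study drug is an AE. Acted-on values should therefore reach Tables 3.2.6, 3.2.7 and 3.2.20.

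**Conclusion.** The gap is real but narrow. Both documents require subjects to be counted by laboratory grade, none of the five planned laboratory tables is titled for it, and the visible text does not record its removal. It touches 19 chemistry and hematology parameters, or 23 with lipids and coagulation.

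Three things would have no aggregate count:

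- high-grade values that were neither acted on nor judged clinically meaningful;
- the split between laboratory Grade 3 and Grade 4;
- laboratory Grades 1 and 2.

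The documents do not allow an estimate of how many subjects this concerns. The conclusion rests on two assumptions: that Appendix E is complete as shown, as SAP 10.1 implies, and that the shift tables follow the layout in 8.3.2. If the standard layout is in fact graded, the point reduces to saying so. It is worth settling before the tables are produced, because it concerns a component of the Phase 1 primary endpoint.

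**What to change.** Make one of two changes to Appendix E:

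1. Add the tables that 8.3.2 already specifies: number and percentage of subjects by worst treatment-emergent CTCAE grade, one for hematology and one for chemistry, with high and low directions separate. In Appendix B, hemoglobin, lymphocytes, calcium, glucose, potassium and sodium are graded both ways.
2. Or retitle and define Tables 3.3.2.1 and 3.3.2.2 as shifts from baseline grade to worst postbaseline grade.

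In either case, state whether the lipid and coagulation parameters are included. If the sponsor did intend to drop the analysis, SAP 10.1 should say so and 8.3.2 should be amended. That removes the contradiction but leaves the Protocol 9.4.3 tabulation undone.

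The cost is small: the algorithm and cut-points are already in the SAP, so the work is a few more standard tables. The downside is a slightly longer abbreviated CSR.

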3.5 ECG			
3.5.9	Summary of Clinically Significant ECG Abnormality	Safety Evaluable	Х

Listings

Listing No.	Title		
2.1 Discontinued Subjects (Subject Disposition)			
2.1.1	Subject Enrollment and Disposition Status		
2.2 Protocol Deviation			
2.2.1	Protocol Deviations		
2.3 Data Ex	2.3 Data Excluded from Efficacy, and/or Safety Analyses		
2.3.1	Analysis Populations		
2.4 Demogr	raphy and Baseline		
2.4.1	Demographic and Baseline Disease Characteristics		
2.4.2.1	Oncology Disease History (Hepatocellular Carcinoma)		
2.4.2.2	Oncology Disease History (Breast Cancer)		
2.4.2.3	Oncology Disease History (Melanoma)		
2.4.2.4	Oncology Disease History (NSCLC)		
2.4.2.5	Oncology Disease History (Renal Cell Carcinoma)		
2.4.2.6	Oncology Disease History (Squamous Cell Carcinoma of the Head and Neck)		
2.4.2.7	Oncology Disease History (Transitional Carcinoma of the GU Tract)		
2.4.2.8	Oncology Disease History (Ovarian)		
2.4.2.9	Oncology Disease History (Gastric Cancer)		
2.4.2.10	Oncology Disease History (Colorectal)		
2.4.2.11	Oncology Disease History (DLBCL)		
2.4.2.12	Oncology Disease History (Adenocarcinoma of the Endometrium)		
2.4.3	Prior Radiation Treatment		
2.4.4	Prior Medications for Cancer		
2.4.5	Prior Surgery		
2.4.6	Medical History		
2.4.7	Prior and Concomitant Medication		
2.5 Study I	Drug Administration		
2.5.1	Study Drug Administration – INCB024360		
2.5.2	Study Drug Administration – MK-3475		
2.5.3	Study Drug Administration for Subjects Who Entered Monotherapy Period – INCB024360		
2.5.4	Study Drug Administration for Subjects Who Entered Retreatment Period – INCB024360		
2.5.5	Study Drug Administration for Subjects Who Entered Retreatment Period – MK-3475		
2.6 Efficacy	2.6 Efficacy		
2.6.1.1	Investigator-Reported Assessment by irRECIST Criteria (Phase 2 only, not including DLBCL)		
2.6.1.2	Investigator-Reported Assessment by Modified Lugano Criteria (Phase 2 only, DLBCL only)		
2.6.2.1	Duration of Response by irRECIST/Modified Lugano Criteria (Phase 2 only, all tumor types)		
2.6.2.2	Duration of Disease Control by irRECIST/Modified Lugano Criteria (Phase 2 only, all tumor types)		
2.6.2.3	Progression-Free Survival by irRECIST/Modified Lugano Criteria (Phase 2 only, all tumor types)		
2.6.2.4	Overall Survival (Phase 2 only, all tumor types)		
2.6.2.5	Target Lesions (Phase 2 only, not including DLBCL)		
2.6.3.1	Investigator-Reported Assessment by RECIST Criteria (Phase 2 only, not including DLBCL)		
2.6.3.2	Investigator-Reported Assessment by Lugano Criteria (Phase 2 only, DLBCL only)		

Listing No.	Title	
2.7 Adverse Events		
2.7.1	Adverse Events	
2.7.3	Liver Function Laboratory Values in Subjects With Aminotransferase (ALT or AST) >=3 x ULN and Bilirubin >=2 x ULN and Alkaline Phosphatase <2 x ULN	
2.7.4	Dose-Limiting Toxicities	
2.7.5	Serious Adverse Events	
2.7.6	Adverse Events Leading to Interruption, Reduction, or Discontinuation of Any Study Drug	
2.7.7	Fatal Adverse Events	
2.8 Labora	tory Data	
2.8.1.1	Clinical Laboratory Values - Hematology	
2.8.1.2	Clinical Laboratory Values - Chemistry	
2.8.2	Abnormal Clinical Laboratory Values	
2.9 Vital Si	2.9 Vital Signs	
2.9.1	Vital Sign Values	
2.10 ECG		
2.10.1	12-Lead ECG Values	
2.12+ Othe	2.12+ Other Data	
2.12.1	PD-L1 Status	

Document Number: IC-STS-SAP-0149 **Title:** INCB 24360-202 SAP Amendment 4

All dates and times are in Eastern Standard Time.

24360-202 SAP Am 4

Approval and Release
